## **PROJECT SUMMARY**

**Rationale:** There is no effective therapy for non-alcoholic fatty liver disease (NAFLD), although intensive calorie restriction is typically recommended but dietary adherence is an issue. The current study aimed to determine the effectiveness and adherence of eight weeks of modified intermittent fasting in the control of NAFLD activity.

**Objective:** Primary objective are to determine the effectiveness of 8 weeks of MACR in changes of BMI, biochemical and ultrasound parameters in NAFLD. The secondary objective is to evaluate the adherence rate of MACR in NAFLD patients.

**Method:** This is a randomized, single-blind controlled trial with 8-weeks modified alternate-day calorie restriction (MACR) as the active intervention and normal habitual diet as control in Hospital Universiti Sains Malaysia with study duration for 24 months. The outcome measures are included changes in BMI, blood lipids, fasting blood sugar, liver enzymes and ultrasonographic measurements of liver steatosis and shear wave elastography (SWE). Per-protocol (PP) and intention-to-treat (ITT) analysis are performed within and between-groups with  $P < 0.05$  as significant.

**Expected outcome:** Specifically, we expected here that MACR regimen resulted in a mean weight loss between 3-5% from baseline after 8 week of intervention thus it is also expected to decreases in several key biomarkers for CAD risk, such as total cholesterol, LDL cholesterol, triacylglycerols and blood pressure. Liver parameter which included liver enzymes, steatosis and fibrosis would also expect to improve after 8 weeks MACR. Additionally, a similar adherence rate is expected to achieve during the MACR regime when compared with other alternate day calorie restriction regime.

**Funding:** USM short term grant (reference no: 304/PPSP/61313173) and Research University Individual (RUI) grant (reference no: 1001/PPSP/812151).

### **Keywords**

Non-alcoholic fatty liver disease; fatty liver; calorie restriction; liver steatosis; liver fibrosis

## **Rationale & background information**

Disease activity and progression of non-alcoholic fatty liver disease (NAFLD) to non-alcoholic steatohepatitis (NASH) and cirrhosis can be highly variable (1), where 2-3% will eventually progress to end-stage liver diseases. With the rising prevalence of metabolic syndrome and obesity, NAFLD has become the most frequent form of chronic liver disease in the West but also in Asia (2, 3).

There are good evidence that weight loss is effective in improving liver histology in NAFLD, for example, Pomrat et al randomised 31 obese patients with NASH into intensive lifestyle changes over 48 weeks versus structured basic education only, and the intensive lifestyle group showed significant improvements in steatosis, necrosis, and inflammation (4). Intense calorie restriction is the recommended form of dietary strategy for management of NAFLD. Even though such intense dietary strategy has proven to be effective (4, 5), some patients find it difficult to adhere and maintain.

On the other hand, intermittent fasting achieves more consistent weight loss by improving adherence (6, 7), as intermittent fasting only requires calorie restriction every other day compared to conventional form of daily calorie restriction (8). Alternate day calorie restriction can be divided into two components, a 'feed day' and a 'fast day' where food is consumed ad libitum for 24 hours period alternating with either complete or partial (modified) calorie restriction for the next 24 hours. Modified alternate-day calorie restriction (MACR), the dietary strategy employed in our study, restricts 70% of an individual's daily requirement of calorie per day (8). There are other forms of intermittent fasting, for example, 2-4 days of ad libitum feeding alternating with 2-4 days of calorie restriction (8-11).

Currently, there are no approved pharmacological therapies for NAFLD, and many guidelines advocate recommendation with a focus on controlling risk factors and lifestyle interventions that include dietary and physical activities. No specific NAFLD trials have evaluated the effectiveness of modified form of intermittent fasting in the control of NAFLD activity. Therefore, our study aimed to determine the effectiveness of 8 weeks of MACR in changes of BMI, biochemical and ultrasound parameters in NAFLD and to evaluate the adherence rate of such dietary strategy.

### **Study goals and objectives**

#### **Research question**

1. Does of MACR associated with improvement of mean liver steatosis and elastography using shear wave elastography in NAFLD patients?
2. Does MACR associated with improvement of biochemical parameter (lipid profile, liver chemistries) in NAFLD patients?
3. Does MACR have a good adherence rate for dietary strategy

**Study goals**

To determine the effectiveness of 8 weeks of MACR in changes of BMI, biochemical and ultrasound parameters in NAFLD and to evaluate the adherence rate of such dietary strategy.

**Primary objective**

To determine the effectiveness of 8 weeks of MACR in changes of BMI, biochemical and ultrasound parameters in NAFLD

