## **Methodology**

### **Participants**

NAFLD patients who attending the Gastroenterology Clinic at Hospital Universiti Sains Malaysia, a tertiary referral centre for the north-eastern Peninsular Malaysia, will be screen from August 2015 till July 2016.

During the first visit, if participants met the selection criteria, informed consent are then taken. Demographic data of participants are recorded. All participants are required to complete a two-week run-in period consisting of maintaining and self-monitoring their usual dietary and daily activities.

[figure not shown]
Participants who fulfilled the selection criteria are randomly assign to the MACR group or the control group after a 2 week run-in period. During the 2 weeks, participants are requiring to keep their body weight stable by maintaining their usual eating habits and their daily activities. Randomization is performed using a random number generator with recruitment aimed for three MACR participants for every control participant by principal investigator. Calculated sample size of 46 participants would achieve a significant difference in studied outcome between intervention and control group using a two-sided test with  $\alpha = 0.05$  and power = 0.8. Participants are blinded after assignment to interventions or control group.

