## **Data management and statistical analysis**

Descriptive statistics are computed for all variables; means with standard deviations (SD) for continuous variables, median with interquartile range (IQR) for ordinal data and frequencies with percentages for categorical variables. Using Kolmogorov-Smirnov analysis, the data were normally distributed if the skewness is within the range of  $\pm 2$  time standard error (SE)

of skewness. Per-protocol (PP) and intention-to-treat (ITT) analysis are performed where comparison is made within-group (post- vs. pre-intervention for each intervention and control group) and between-group (MACR vs. control). Missing data are imputed using multiple imputation method. Independent *t*-test is used to analyse changes in weight, liver chemistry, lipid profile variables, fasting blood sugar and ultrasonographic changes of liver steatosis and fibrosis between the MACR and control group. SPSS version 22 (SPSS Inc., Chicago, United States) is used for all statistical analysis. All *P* values quoted were two-sided with  $P < 0.05$  considered as statistically significant. Sample size is 46 participants with 80% power of the study.

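### About ten outcomes share the primary objective, each tested at unadjusted P<0.05 with none designated primary, and the 46 participants and 80% power are tied to no named outcome

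*Combined protocol and SAP*

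**What the plan says.** The Primary objective section reads: "To determine the effectiveness of 8 weeks of MACR in changes of BMI, biochemical and ultrasound parameters in NAFLD". The Objective paragraph of the Project Summary says the same. The only secondary objective is adherence.

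The Procedures section lists the measures behind those three domains:
- BMI, calculated from weight and height;
- seven blood measures: HDL, LDL, triglycerides, total cholesterol, fasting sugar, ALT and AST;
- two ultrasound measures: a steatosis grade from 0 to 3, and SWE stiffness in kPa.

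Under Data management and statistical analysis, the two arms are compared by a t-test for independent samples, which "is used to analyse changes in weight, liver chemistry, lipid profile variables, fasting blood sugar and ultrasonographic changes of liver steatosis and fibrosis". The same section states: "Per-protocol (PP) and intention-to-treat (ITT) analysis are performed where comparison is made within-group", and goes on to add between-group comparisons. All P values are two-sided with a 0.05 threshold. On missing data: "Missing data are imputed using multiple imputation method".

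On size, the Participants section states: "Calculated sample size of 46 participants would achieve a significant difference in studied outcome between intervention and control group", at two-sided alpha 0.05 and power 0.8, "with recruitment aimed for three MACR participants for every control participant". The analysis section adds: "Sample size is 46 participants with 80% power of the study".

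**The concern.** Nothing in the objectives, sample-size or analysis text says which result decides the trial. About ten outcomes are co-equal. Two analysis sets and two kinds of comparison (change within each arm, and difference between arms) stand side by side, with no lead, no adjustment and no rule for success.

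Followed as written, the plan allows effectiveness to be claimed on whichever outcome crosses 0.05. The chance of that under no effect is then several times the nominal 5%.

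The power statement does not help. It names no outcome, difference or SD, so a reader cannot tell which null results are informative and which merely reflect a small trial.

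**Working it through.** **1. Count of outcomes.** BMI/weight (counted once) 1 + blood measures 7 + ultrasound measures 2 = 10. If fasting sugar is left out, because research question 2 illustrates the biochemical parameters only with lipids and liver chemistries, the count is 9. The objective names BMI while the t-test sentence names weight; counting both would give 11.

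**2. The plan's own figure.** The 46 cannot be reproduced, because no difference, SD or dropout rate is given. The nearest quantity is the expected 3-5% mean weight loss. That is a within-arm expectation for the diet group, with no SD, no control value and no stated link to 46.

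**3. Chance of at least one false positive, all outcomes null, one between-group test each.**
- Independent tests: 1 - 0.95^10 = 0.401; 1 - 0.95^9 = 0.370.
- Correlated outcomes: simulated normal changes with a common pairwise correlation and pooled t-tests at 34:12 (200,000 trials for ten outcomes, 100,000 for nine).

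| Assumed correlation | 10 outcomes | 9 outcomes |
|---|---|---|
| 0 (exact) | 40% | 37% |
| 0.3 | 35% | 33% |
| 0.5 | 29% | 27% |
| 0.7 | 22% | 21% |

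At a correlation of 0.8, a normal approximation for ten outcomes gives about 17%. The correlations are assumptions, and the simulation treats the 0-3 steatosis grade as if it were normal.

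**4. Choice between per-protocol and intention-to-treat.** For one null outcome, the chance that either set is significant was simulated with 34:12 for intention-to-treat and 30, 27 or 24 of the 34 MACR participants kept per protocol. This assumes exclusion at random. Results: 5.9%, 6.3% and 6.6%. The number of outcomes, not the number of analysis sets, drives the inflation.

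**5. What 46 participants can detect.** Exact 3:1 would be 34.5:11.5, so 34:12 and 35:11 are used. For a continuous outcome the normal approximation is d = (1.960 + 0.842) × √(1/n1 + 1/n2).
- 34:12: 2.802 × 0.336 = 0.94 SD; noncentral t gives 0.962 SD.
- 35:11: 2.802 × 0.346 = 0.97 SD; noncentral t gives 0.990 SD.
- For comparison, 23:23 gives 0.845 SD by noncentral t.

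Power at 34:12 is 64% for 0.8 SD and 31% for 0.5 SD.

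**6. Losses.** The plan states no allowance. If the planned imputation recovered no information, power at 0.962 SD would be 76% (31:11) or 71% (27:10). If only MACR participants were lost, it would be 78% (30:12) or 77% (27:12). These loss patterns are assumptions.

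**7. Keeping all ten co-equal with adjustment.** Bonferroni gives 0.05/10 = 0.005 per test. By the normal formula at 34.5:11.5, 46 participants have 80% power for 0.954 SD at alpha 0.05; at 0.005 this falls to about 50%. Restoring 80% would take about 80 participants.

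**The case against.** **The objective never says that one positive result is enough.** It could mean improvement in all three domains. Under that reading the false-positive risk falls and power becomes the main problem. This stands as a condition on the 22-40% range. It does not remove the concern: the plan does not state the all-domains rule either, and whoever writes the report may choose.

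**The 40% figure needs independence.** Lipid measures are related to each other, and so are the two liver enzymes. This is fair, and 40% is an upper figure. Even at an assumed correlation of 0.7 the rate is 22%, more than four times nominal.

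**The 46 may rest on the 3-5% weight-loss expectation, and may not have assumed 3:1.** Both are possible and neither is stated. The charge is that 46 cannot be checked, not that it is wrong. Restating it as 0.96 SD discloses what the trial can detect; it does not justify that difference as plausible.

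**SWE has no special claim as a fallback outcome.** True: research question 1 pairs it with steatosis, the objective lists BMI first, and weight loss is the only expectation with a number. SWE is an example only.

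**It may be too late.** Screening was planned for August 2015 to July 2016. If outcome data have been seen, a choice made now is post hoc.

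**Conclusion.** The concern holds and should be fixed before any effectiveness claim is made. About ten outcomes are jointly primary, with no lead outcome, population or comparison and no adjustment. If any one significant between-group result counts as success, the false-positive rate for the primary objective is 40% under independence and 22-35% at assumed correlations of 0.7 to 0.3, roughly four to eight times the nominal 5%. The choice of analysis set adds little by itself.

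The 80% power can be traced to no outcome. For a continuous outcome at about 3:1, it corresponds to a difference of 0.96 to 0.99 SD. A null result would say little about differences near 0.5 SD, where power is 31%.

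**What to change.** 1. **Name one primary outcome and one primary analysis before outcome data are seen.** The outcome should be the one for which 46 was calculated. If that cannot be identified, choose a single continuous outcome, for example SWE in kPa, and give the reason. The analysis should be the between-group intention-to-treat comparison of change, with the multiple imputation already planned, at two-sided 0.05.
2. **Make every other outcome secondary.** Either adjust them by Holm's method or report estimates with 95% confidence intervals and no significance claim. Label the per-protocol analysis supportive and the within-group tests descriptive.
3. **Restate the power for the named outcome.** Give the detectable difference at the planned 3:1 allocation (about 0.96 SD at 34:12 if continuous), the SD assumed, and why that difference is plausible. Label any loss rate as an assumption. If 46 was calculated for the 0-3 steatosis grade, give the power of an ordinal comparison instead.

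The cost is protocol and SAP wording, with no extra patients. The other outcomes lose confirmatory status, and the power statement will look less favourable. If outcome data have already been seen, the choice must be reported as post hoc.

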**Secondary objective**

To evaluate the adherence rate of MACR in NAFLD patients

**Study Design****Type of study**

Randomized control trial

**Study Duration and location**

Study Location : Gastroenterology Clinic and Radiology Department Hospital USM.

Study Duration : 24 months

**Sampling Population and sample**

Reference Population:

- Non-Alcoholic Fatty Liver Disease (NAFLD)

**Source Population**

Gastroenterology Clinic in Hospital Universiti Sains Malaysia (HUSM), Kota Bharu, Kelantan  
NAFLD patient

**Sampling Frame**

Inclusion criteria

1. Age ranges 18 to 70 years old
2. Baselines Ultrasound show evidence of fatty liver
3. Elevated alanine aminotransferase (ALT) or aspartate aminotransferase (AST) values (ALT>41 or AST>34U/L)

Exclusion criteria

1. Medically or surgically ill patients who cannot consent
2. Complicated chronic liver disease with portal hypertension
3. Significant alcohol consumption (1 standard drink per day)
4. Contraindications to calorie restriction
5. Pregnancy
6. Engagement in an active weight loss program
7. Taking weight-loss medication, substance abuse
8. Significant psychiatric problems

Withdrawal criteria

1. Subject who unable to tolerate alternate daily fasting intervention during the trial
2. Patient own choice

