### **Interventions**

#### **MACR group**

For a total of 8 weeks, participants in this group need to restrict 70% of their energy needs over 24 hours on a calorie restriction day alternate with a feeding day for the next 24 hours, where participants allowed eating whatever they wish (ad libitum). The calorie restriction and feeding days begin at 9am each day, and on the calorie restriction day, meals are consumed between 2pm and 8pm to ensure that each participant underwent the same duration of calorie restriction. The MACR protocol is shown in Figure 1. On each calorie restriction day, participants are allowed to take energy-free beverages, tea, coffee, and sugar-free gum and encouraged to drink plenty of water. Diet plans are not provided to participants but are self-selected using detailed individualized food portion lists, meal plans, and recipes. To ensure maximal adherence to dietary plan, participants received phone calls from the investigator ([name]) and 2-weekly appointments (total four appointments) with a dietician described below. Adverse experiences are assessed every 2 weeks until 1 week after the completion of trial.

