**Figure 1 MACR protocol for the 8 weeks duration**

### **Assessment of dietary plan adherence**

[figure not shown]
A designated dietician ([name]) will provide education to participants regarding calorie restriction and help to monitor their dietary compliance. Adherence to intervention is assessed via a diet diary and dietary recall. The diary is collected and reviewed by the dietician every 2 weeks. If the diary indicates that the participants eat an extra calorie on a fasting day, that day is labelled as “not adherent.” If the diary revealed that the participant did not eat any extra food item, that day is labelled as “adherent.” Adherence data are assessed each week as 1) absolute adherence (number of adherent days with diet) and 2) percentage of adherence calculated by applying the following formula for adherence in percentage. The formula is shown below.

$$\frac{\text{Number of fast day's adherent}}{\text{Number of fast days in week}} \times 100$$

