### **Control group**

All participants in the control group will continue their usual habitual diet for 8 weeks. No specific dietary advice or educations are provided throughout the entire trial.

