## **Procedures**

A standardized calibrated balance (Secca, ZT-120, and Hamburg, Germany) will be used to measure weight of participants in light clothing at each visit. A wall-mounted stadiometer (Secca, ZT-120, Hamburg, Germany) is used to measure height (in m), and together with weight (in Kg), body mass index (BMI) is calculated. Waist circumferences are measured with the participants standing, and with the measuring tape kept horizontal and measured at a level midway between the superior aspect of the iliac crests and the lower lateral margins of the ribs.

Blood samples - 8-10 hours of fasting blood samples are collected at 8-10 am at baseline and within 1 week post intervention for biochemical analysis. High-density lipoprotein (HDL), low-density lipoprotein (LDL), triglycerides (TG), total cholesterol, fasting blood sugar and liver enzymes (alanine aminotransferase, ALT and aspartate aminotransferase, AST) are measured.

Ultra-sonographic measurements including liver steatosis and shear wave elastography (SWE) are performed with the SuperSonic Imagine's Aixplorer® Ultrasound machine (Super Sonic Image, Aix-en Provence, France). All measurements are performed by a single sonographer ([name]) where the inter-observer agreement level with another experienced sonographer ([name]) is 85%. Hepatic steatosis is graded as normal (grade 0), mild (grade 1), moderate (grade 2) and severe (grade 3) based on visual analysis of intensity of echogenicity with an appropriate gain setting based on standardised parameter (13-14). Homogenous echotexture and echogenicity equal or slightly more than the renal cortex and spleen are characteristics of a normal liver. Liver echogenicity would be higher than the renal cortex and spleen if there was hepatic steatosis.

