## **1. Subject vulnerability**

1.1 The participants who involved in the study will be provided comprehensive explanation regarding the study procedure, any known adverse reactions, anticipated benefits and potential hazards of the study. If the subject is under my care as a doctor, the patient will be given full freedom to participate or not without affecting her medical condition management and care.

1.2 Participants will not get vulnerable to the study as data obtained from this study does not identify participants individually. Besides that, the data will be independent and will not be used for any achievement assessment and decision related to work

1.3 In addition, participants are given option to terminate their involvement in the study at any time without penalty or loss of benefits if they want to stop. A list of contact number of the investigators will be included in the participants information leaflet and they can directly contact the investigator if they have any queries or opt to cease the study.

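### Being unable to tolerate fasting is a withdrawal criterion only MACR participants can meet, and no readable text gives those withdrawn an 8-week blood or ultrasound assessment for ITT

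*Combined protocol and SAP*

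**What the plan says.** The Sampling Frame section sets out inclusion, exclusion and withdrawal criteria. There are two withdrawal criteria. The first is "Subject who unable to tolerate alternate daily fasting intervention during the trial"; the second is the patient's own choice. The right to leave is stated again under 1. Subject vulnerability: "participants are given option to terminate their involvement in the study at any time without penalty".

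The arms differ in exposure. For MACR: "For a total of 8 weeks, participants in this group need to restrict 70% of their energy needs over 24 hours" on restriction days, alternating with free-eating days. For controls: "All participants in the control group will continue their usual habitual diet for 8 weeks".

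Under Procedures, fasting bloods are "collected at 8-10 am at baseline and within 1 week post intervention for biochemical analysis". The balance is used to "measure weight of participants in light clothing at each visit". Steatosis grading and shear wave elastography are described without a timetable, and no interim scan is mentioned.

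The Data management and statistical analysis section plans per-protocol and ITT analyses, within and between groups. On missing values it says only "Missing data are imputed using multiple imputation method"; it gives no imputation model, missingness assumption or sensitivity analysis.

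Nothing in the readable text separates stopping the diet from leaving the trial, or says that withdrawn participants return for the end assessment. The flow diagram (Figure 2) could not be seen.

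**The concern.** The first criterion sits beside inclusion and exclusion, so its natural reading is that the participant leaves the trial, not just the diet. It is not needed to protect the right to leave, which the second criterion and the ethics section already give to both arms.

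Followed as written, the plan loses outcomes in one arm for a reason tied to the treatment. People who cannot tolerate fasting may differ in outcome from those who can, and data from completers cannot test that. If the imputation model includes arm, it fills these participants in largely from MACR completers. The ITT estimate then moves towards the completer result and loses much of what should distinguish it from per-protocol. The situation is foreseeable: the Problems Anticipated section itself names compliance with the diet as a difficulty.

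Liver enzymes, lipids, glucose and ultrasound are the most exposed. Weight is partly protected, because weights from visits before withdrawal can inform the imputation.

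**Working it through.** **1. The plan's own figure.** The plan states 46 participants, 3:1 allocation, two-sided alpha 0.05 and power 0.8. The 46 cannot be reproduced, because no effect size, SD or dropout rate is given. It can be turned round to give the difference it would detect, which serves here only as a yardstick.

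- Split: 46 × 0.75 = 34.5 and 46 × 0.25 = 11.5; 34 MACR and 12 controls are used.
- Normal approximation: (1.960 + 0.842) × √(1/34 + 1/12) = 2.802 × 0.3358 = 0.941 SD.
- Noncentral t: 0.962 SD (0.990 SD at 35 v 11).

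**2. What an early stopper would contribute.**

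| Outcome | Planned timing | Participant withdrawn early |
|---|---|---|
| Bloods | Baseline and within a week after the intervention | No post-baseline sample, or one soon after stopping that is not an 8-week value |
| Ultrasound | No timetable; no interim scan mentioned | No stated 8-week scan |
| Weight | Each visit | Weights up to withdrawal; no stated 8-week weight |

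**3. Shift in the between-group difference.** Assume all controls are measured, withdrawn MACR participants have no end value, and imputation includes arm. Let e be the completer effect, g the completer-minus-withdrawn gap in SD (positive when completers do better), and k the number withdrawn of 34.

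- MACR effect with everyone measured: e − (k/34)g
- MACR effect with the withdrawn imputed from MACR completers: e
- Shift: (k/34) × g

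Both k and g are assumptions. Percentages are of 0.962 SD.

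| k (share of 34) | g = 0 | g = 0.5 | g = −0.5 | g = 1 |
|---|---|---|---|---|
| 3 (0.088) | 0 | 0.044 (4.6%) | −0.044 | 0.088 (9.2%) |
| 7 (0.206) | 0 | 0.103 (10.7%) | −0.103 | 0.206 (21.4%) |
| 10 (0.294) | 0 | 0.147 (15.3%) | −0.147 | 0.294 (30.6%) |

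The g = 1 column is extreme. With a completer effect of 0.96 SD, it puts the withdrawn at 0.96 − 1 = −0.04 SD, slightly below the control mean, so they keep no benefit from any weeks of fasting.

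**4. Dependence on the imputation model.** Without an arm term, the withdrawn would be filled in from everyone observed. With k = 10 and e = 0.96, the observed mean is (24 × 0.96 + 12 × 0)/36 = 0.64. The imputed MACR mean is (24 × 0.96 + 10 × 0.64)/34 = 0.866.

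- g = 0: the full-follow-up mean is 0.96, so the shift is 0.866 − 0.96 = −0.094 SD.
- g = 1: the full-follow-up mean is 0.96 − 0.294 = 0.666, so the shift is 0.866 − 0.666 = +0.200 SD.

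Size and sign therefore depend on the unstated model as well as on the outcomes of those withdrawn.

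**The case against.** The case for leaving the plan alone has several parts.

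- **The criterion speaks of not tolerating the intervention; it does not say that follow-up ends.** Naming ITT beside per-protocol is compatible with continued observation. That is fair, but the heading is withdrawal, and no readable sentence provides the observation.
- **Blood sampling within a week after the intervention could mean after that participant's own last day on the diet.** This reading is open, and it means one cannot say that early stoppers have no post-baseline bloods. It does not close the gap: a sample at week 3, say, is not comparable with controls sampled after 8 weeks.
- **Adverse experiences are assessed every two weeks until a week after completion.** This is contact, but it appears in the MACR section, is not an outcome visit, and is not said to cover those withdrawn.
- **Figure 2 may show follow-up after withdrawal.** It may. That limits the claim to the readable text and leaves a need to reconcile the wording.
- **Multiple imputation is a legitimate method.** It is, but it does not replace measurements that could be obtained when missingness may depend on the unseen outcome.

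Three stronger readings are tempting and not supported. First, a reader might infer that ITT is biased in favour of MACR. The documents settle neither direction nor size, and control dropout by own choice could add to or offset any shift. Second, a reader might infer a shift of about a third of the detectable difference either way. The 31% arises only if the withdrawn do 1 SD worse; the largest negative case worked is −0.147 SD, or 15%. A larger one would need those who could not tolerate the diet to finish well ahead of those who completed it, and nothing in the documents points there. Third, a reader might infer that the adherence rate is inflated. The formula's denominator is "Number of fast days in week", and nothing says that fast days after stopping are excluded, so no defect is shown there.

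**Conclusion.** The point holds as a cheap improvement, with medium confidence. It establishes that the criterion applies to one arm only, that no readable text secures an 8-week blood or ultrasound value for those who meet it, and that multiple imputation is the only stated remedy for missing data.

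It does not establish that the ITT result will be wrong. At 3 withdrawn and a 0.5 SD gap, the shift is negligible; at 10 withdrawn and that gap, it is about 15% of what the trial can detect; the 31% figure is an outer bound on deliberately severe assumptions. These figures rest on assumed withdrawal numbers and gaps, full control follow-up, an imputation model with an arm term, and a yardstick back-solved from the stated power. The case for acting is that measuring these participants removes most of the dependence on an assumption the data cannot check.

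**What to change.** Neither change alters when a participant may stop fasting.

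1. In the Sampling Frame section, reword the withdrawal criteria so that stopping the diet is not withdrawal from the trial. Leaving the trial remains the participant's own choice, as the second criterion and 1. Subject vulnerability already provide.
2. In Procedures, state that everyone randomised who has not withdrawn consent has the planned weight, blood and ultrasound assessments 8 weeks after the start of the allocated diet period, whether or not still on the diet. Analyse them as randomised in ITT, and keep multiple imputation for those who cannot be measured.

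If Figure 2 already shows follow-up after withdrawal, reconcile both sections with it instead.

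The cost is two wording changes and the already planned end assessment for a few more people (3 to 10 in the illustration). Some who stop will decline to attend, and the reported effect may be less favourable.
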